9 INVESTIGATIONAL PLAN

9.1 Overall Study Design and Plan

This is a multicenter, randomized, double-blind, placebo-controlled, parallel-group study in obese adolescents ages 12 to 17 years. Approximately 260 subjects will be randomized in a 1:1 ratio to Belviq XR 20 mg QD (130 subjects) and placebo (130 subjects). Subjects will be stratified by sex. Subjects will receive Belviq XR 20 mg or matched placebo QD in a 1:1 ratio for up to 52 weeks. A recruitment plan will be developed to ensure at least 20% of younger subjects (12 to 13 years of age) are enrolled in the study. Throughout the duration of the study, subjects will be encouraged to adhere to a lifestyle modification program that includes a standardized, age-appropriate diet and exercise counseling (see [Appendix 2](#)). (revised per Amendments 02 and 03)

The study will consist of 2 phases: Prerandomization and Randomization. The Prerandomization Phase will last up to 30 days and consists of 1 visit during which subjects will be screened for eligibility. The Randomization Phase consists of a Treatment Period and a Follow-Up Period. The Treatment Period will last for a maximum of 52 weeks, with visits at Weeks 1, 5, 8, 12, 20, 28, 36, 44, and 52; the Follow-Up Period will extend from the End of Treatment (EOT) visit to the End of Study (EOS) visit.

Subjects who screen fail can be rescreened only once. All subjects will continue in the study until the 52-week evaluation is completed. Subjects who discontinue treatment prematurely will be followed up until study completion. All attempts will be made to capture height and weight in all subjects whether or not they are still on study drug at the end of the study. (revised per Amendments 03 and 04)

Study sites will be selected to ensure adequate representation of adolescents of ethnic and racial minorities. (revised per Amendment 03)

A Data Monitoring Committee (DMC) will be established to monitor and conduct periodic safety review of unblinded data. DMC members will be chosen based on their expertise in evaluating these clinical events. A separate DMC charter will be established. (revised per Amendment 03)

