9.5.2.3 Total Volume of Blood Sampling

[Table 3](#) presents the number of blood samples and the total volume of blood that will be collected throughout the study. Additional samples may be taken at the discretion of the investigator if the results of any tests fall outside reference ranges or clinical symptoms necessitate testing to ensure subject safety.

Table 3 Summary of Blood Sample Volumes (revised per Amendments 01, 03, and 04)

	Sample Volume per Collection (mL)	Number of Collection Time Points	Total Volume Collected (mL)
Clinical laboratory tests (Chemistry and Hematology)	5	Screening: 1 Visits 2, 3, 4, 6, 8, 11 (EOT), EOS or ED	5×8=40
T4, TSH	2.5	Screening: 1 Visits 2, 8, 11 (EOT), or ED	2.5×4=10
Testosterone, estradiol	0.5	Visits 2, 8, 11 (EOT)	0.5×3=1.5
AM serum cortisol	0.5	Visits 2, 11 (EOT), or ED	0.5×2=1
Serum OC and PICP, Hydroxy-proline; Fasting lipid panel (HDL cholesterol, LDL cholesterol, total cholesterol, triglycerides)	8	Visits 2, 8, 11 (EOT), or ED	8×3=24
Fasting Prolactin, FPG, fasting insulin, and HbA _{1c} sampling	5	Screening: 1 Visits 2, 6, 8, 11 (EOT) or ED	5×6=30
PK/PD blood sampling	4	Visits 6, 8, and 11 (EOT) or ED (2 samples each); Visit 9 (1 sample only)	4×7=28
Total			134.5

ED= early discontinuation from study, EOS = End of Study, EOT = End of Treatment, FPG = fasting plasma glucose, HbA_{1c} = hemoglobin A_{1c}, OC = osteocalcin, PD = pharmacodynamic, PICP = carboxyterminal propeptide of type I procollagen, PK = pharmacokinetics, T4 = thyroxine, TSH = thyroid stimulating hormone.

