9.7.1.6 Efficacy Analyses

The FAS will be used as the primary analysis set for all efficacy analyses, while the PP will be used as a supportive analysis. Unless specified otherwise, a 2-sided $\alpha=0.05$ significance level will be used for all efficacy analyses.

Primary Efficacy Analysis

The primary efficacy endpoint is the change in BMI from baseline to Week 52. The change from baseline in BMI will be analyzed using analysis of covariance model (ANCOVA) with factors of treatment, sex (male and female) as fixed effect, and the baseline age and BMI as covariates. The missing values will be imputed using a pattern mixture model utilizing multiple imputation (MI) assuming the missing values are missing not at random (MNAR). The missing values will be imputed at each visit using all available values including the retrieved measurement from the postdiscontinuation data. The details of the analysis model and missing value imputation method will be further described in the SAP.

In addition, the following analyses will also be considered as sensitivity analyses:

- PP analysis: The same primary efficacy analyses described above will be repeated based on the PP.
- Change from baseline in standardized BMI score (Z-score): The same primary efficacy analyses described above will be repeated using Z-score.

Subgroup analyses and additional sensitivity analyses, if appropriate, may also be performed and will be described in the SAP.

Key Secondary Efficacy Analysis

The key secondary efficacy endpoint is the proportion of subjects achieving at least a 5% BMI reduction at Week 52. The secondary efficacy endpoint will be analyzed only if the test for the primary efficacy endpoint is statistically significant.

The proportion of subjects achieving at least a 5% BMI reduction at Week 52 will be analyzed using a logistic regression model with factors of treatment, and sex (male and female), and baseline BMI as a covariate using FAS. Subjects with any missing assessment at Week 52 will be considered as treatment failures in this analysis.

Other Secondary Efficacy Analyses

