Unless specified, for all other secondary efficacy endpoints, the continuous variables will be analyzed using mixed effect model repeated measurement analysis (MMRM) on the FAS for study treatment compared to placebo, as appropriate. The model will include all data and will include treatment, time, and the interaction of treatment by time as fixed effects, with adjustment for sex (male versus female), BMI and age at baseline, and subject as a random effect. (revised per Amendment 03)

Treatment by time interaction will be used to construct the treatment comparisons at a specific time. The MMRM model assumes that the missing data are missing at random and makes use of all available data even if a subject has missing data at some postbaseline visits. An unstructured covariance matrix will be used, and if the model fails to converge, then an autoregressive matrix will be used. (revised per Amendment 03)

Categorical variables will be analyzed using the Cochran Mantel Haenszel test, Chi-square test, or logistic regression as appropriate. Additional analysis may be performed as needed using appropriate statistical methodologies as specified in SAP.

Subgroup analyses will be performed on the primary efficacy endpoint, including sex (male and female), race (American Indian or Alaska Native, Asian, Black or African American, Native Hawaiian or other Pacific Islander, or White), and age. Additional subgroups may be explored, if deemed necessary. (revised per Amendment 03)

No adjustment for multiplicity is planned for other secondary endpoints, subgroup, and sensitivity analyses.

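### The secondary MMRM pairs a random subject effect with an unstructured covariance, which is one parameter too many, and its only fallback is an autoregressive matrix of unstated form that can understate the Week 52 standard error

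*Protocol*

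**What the plan says.** Section 9.7.1.6, under Other Secondary Efficacy Analyses, sets the scope: "Unless specified, for all other secondary efficacy endpoints, the continuous variables will be analyzed using mixed effect model repeated measurement analysis (MMRM"). The fixed effects are treatment, time and their interaction. The adjustment terms end with "BMI and age at baseline, and subject as a random effect". Comparisons at a visit come from the interaction: "Treatment by time interaction will be used to construct the treatment comparisons at a specific time". The covariance rule is "An unstructured covariance matrix will be used, and if the model fails to converge, then an autoregressive matrix will be used". It gives no order for the autoregressive structure. It does not say whether the variances are common or visit-specific, whether correlation depends on visit number or elapsed time, or whether the random effect stays in the fallback model.

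Section 9.1 gives the schedule: "with visits at Weeks 1, 5, 8, 12, 20, 28, 36, 44, and 52". Not every endpoint is measured at each visit. By Table 2 the post-baseline treatment visits number nine for BMI, blood pressure and heart rate, five for waist circumference (Weeks 5, 12, 28, 36, 52), three for glucose, insulin and HbA1c (Weeks 12, 28, 52) and one for DEXA (Week 52). Lipids have two (Weeks 28 and 52); Table 3 lists the collections as "Visits 2, 8, 11 (EOT), or ED".

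For these endpoints, "No adjustment for multiplicity is planned for other secondary endpoints, subgroup, and sensitivity analyses".

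**The concern.** There are two linked weaknesses, both in wording that the protocol fixes.

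First, an unstructured within-subject matrix is already as general as a covariance can be. A random intercept adds the same constant to every element, and the matrix can absorb it. The likelihood therefore has a flat direction. Software may return a boundary solution, a singular Hessian or a failure to converge. The last of these sends the analysis to the fallback, even where the unstructured model alone would have fitted.

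Second, the fallback goes in one step from full generality to a matrix that is named only by family. A homogeneous AR(1) has one variance for all visits and a correlation set by visit order. The visits are 3 to 8 weeks apart, and a change in BMI after 1 week is unlikely to vary as much as a change after 52 weeks. A Week 52 comparison would then borrow the small early variances. At stake are the confidence intervals and nominal p-values of endpoints such as percentage change in BMI. The unstated form also leaves a choice open after the data are seen, and that choice can move the standard error by about a third.

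**Working it through.** **Inputs.** Week 52 SD of change in BMI 2.2 kg/m² (variance 4.84), 130 per arm and 40% dropout, from section 9.7.2; 20% missing at Week 52 as the alternative, from the retention target in section 9.5.1.3; visits from section 9.1 and Table 2; two-sided 5% level from section 9.7.1.6. The path of the variance before Week 52 is my assumption, because the protocol gives only one SD.

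**The plan's own figure.** The protocol states no figure for the MMRM. Its primary power statement reproduces: 0.6 × 130 = 78 per arm; SE = 2.2 × √(2/78) = 0.352; 1/0.352 − 1.96 = 0.88; power = Φ(0.88) = 81%, against the stated minimum of 80%.

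**Step 1: identifiability.** With random-intercept variance s, unstructured matrix Σ and J the matrix of ones, the marginal covariance is V = sJ + Σ. For any small d, (s − d)J + (Σ + dJ) gives the same V. With q visits, Σ has q(q+1)/2 parameters, and V can identify no more than that.

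| Post-baseline visits | Unstructured alone | With random intercept | Identifiable |
|---|---|---|---|
| 9 | 45 | 46 | 45 |
| 5 | 15 | 16 | 15 |
| 3 | 6 | 7 | 6 |
| 2 | 3 | 4 | 3 |

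There is always exactly one surplus parameter. V is the same along the flat direction, so a fit that is obtained gives the same treatment estimates as the unstructured model alone.

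If the random effect is kept in a homogeneous AR(1) fallback, there are three covariance parameters. These are identifiable with three or more visits. With the two lipid visits, only one variance and one covariance can be learned, so the model is again one parameter over.

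**Step 2: homogeneous AR(1), by hand.** As a first approximation the common variance is the average over visits. The ratio of reported to true Week 52 SE is the square root of (average variance / Week 52 variance), and the actual error rate is 2 × [1 − Φ(1.96 × ratio)].

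- Variance proportional to t: the nine weeks sum to 206, so the average is 22.9; 22.9/52 = 0.44; ratio 0.66; error rate 19%.
- Variance proportional to √t: the roots sum to 39.1, so the average is 4.35; 4.35/7.21 = 0.60; ratio 0.78; error rate 13%.

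**Step 3: fitted AR(1).** For a random walk plus measurement error, scaled to variance 4.84 at Week 52, the limiting likelihood fit of AR(1) uses a variance of about 2.35. The ratio is √(2.35/4.84) = 0.70 and the error rate 17%. Taking the limiting fit with monotone, completely random dropout of 20% or 40%, over several growth patterns, gives:

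| Assumed variance of change | Schedule | Reported / true SE | Actual error of a 5% test |
|---|---|---|---|
| Growing | 9 visits | 0.65–0.75 | 14–20% |
| Growing | waist, 5 visits | 0.68–0.80 | 12–18% |
| Growing | glucose and insulin, 3 visits | 0.71–0.84 | 10–16% |
| Growing | lipids, 2 visits | 0.80–0.92 | 7–12% |
| Constant | all of these | 1.00–1.01 | about 5% |
| Falling | all of these | 1.06–1.36 | 0.8–3.8% |

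Other correlation assumptions with growing variance at nine visits give 0.69–0.77 and 13–17%. In absolute terms, at nine visits with 40% dropout and growing variance, AR(1) reports an SE of 0.222–0.236 where the true SE of that estimate is 0.326–0.342. Keeping the random intercept in the AR(1) model does not help (0.64–0.75).

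**Step 4: after the change.** The unstructured matrix alone is identified (45 of 45 at nine visits) and gives a Week 52 SE of about 0.32–0.33 with 40% dropout. Heterogeneous AR(1) has a ratio of 0.88–1.10. Its error rate is about 3 to 8% at nine visits with 40% dropout. That is much closer, but not exact, which is why a sandwich standard error is still wanted.

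**The case against.** A reader might infer that the protocol prescribes a homogeneous AR(1) and so understates the Week 52 standard error. The text does not support that. It names an autoregressive matrix and nothing more, and a heterogeneous or time-based version fits the same words. Nor does the protocol say that the variance of change grows. This is plausible for BMI, but nothing in the document suggests it for blood pressure, heart rate or glucose. With constant variance the problem vanishes, and with falling variance the test is conservative. This objection stands, and the size of the effect has to be stated as conditional.

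A reader might also take an error rate near 17% as that of the planned analysis. It is not. Three things must coincide: the unstructured fit fails, the homogeneous form is chosen, and the variance grows. How often the first would happen cannot be estimated from the documents. It is less likely with two or three visits, where the unstructured matrix is small. For DEXA, with one post-baseline scan, the fallback is irrelevant.

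It can be said, too, that naming subject as a random effect is often loose wording for treating the subject as the unit of repeated measurement. If that was meant, there is no redundancy, and the phrase should go because it says something else.

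Finally, the exact autoregressive form, robust variances and the degrees-of-freedom method are commonly left to the SAP, which is not shown. I therefore make no point of degrees of freedom. The random effect and the single-step fallback are different: the protocol states them, and as stated they are poor rules.

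**Conclusion.** The point holds in a limited form. Without any assumption, the model as written carries one unidentifiable covariance parameter on every schedule, and that redundancy can set off the protocol's own fallback. It does not bias the treatment estimates when a fit is obtained.

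The fallback is fixed badly, because one of its natural readings can be seriously wrong. Under homogeneous AR(1) with variance growing to Week 52, the nine-visit standard error is too small by roughly 25 to 35%, with a type I error of about 13 to 20%; the effect is smaller for endpoints with fewer visits. These figures rest on an assumed variance path and on completely random dropout.

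Only the continuous other secondary endpoints are affected. The primary endpoint uses ANCOVA with multiple imputation and the key secondary uses logistic regression. The affected endpoints are supportive and carry no multiplicity adjustment, so nothing offsets an inflated error rate. The change is worth making because it costs almost nothing.

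**What to change.** In section 9.7.1.6, delete the random subject term from the unstructured MMRM. Replace the single autoregressive fallback with an ordered list of structures that keep visit-specific variances, for example heterogeneous Toeplitz and then heterogeneous AR(1), taking the first that converges. State that empirical (sandwich) standard errors are used whenever a fallback applies, and carry the same text into the SAP.

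The cost is a few lines of wording and slightly less efficient standard errors if a fallback is used. No data collection or visit changes.

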9.7.1.7 Pharmacokinetic, Pharmacodynamic, Pharmacogenomic, and Other Biomarker Analyses

9.7.1.7.1 PHARMACOKINETIC ANALYSES

Lorcaserin plasma concentration-time data will be subjected to population PK analysis using nonlinear mixed effects modeling. The effect of covariates, such as baseline characteristics or demographics, on PK will be explored. Derived exposure parameters such as the maximum observed concentration and the area under the concentration-time curve from time 0 to 24 hours at steady-state will be calculated from the final PK model using individual

posterior estimates of the PK parameters and from dosing history. The PK analysis set will be used for this analysis.

9.7.1.7.2 PHARMACODYNAMIC ANALYSES

Change from baseline in BMI will be assessed as the PD endpoint. The PD analysis set will be used for this analysis.

Other assessments (eg, percentage of BMI change, proportion [%] of subjects achieving $\geq 5\%$ and $\geq 10\%$ BMI reduction, and change in waist circumference from baseline) will also be assessed as part of the PD analysis. The PK/PD analysis set will be used for this analysis.

9.7.1.7.3 PHARMACOKINETIC/PHARMACODYNAMIC ANALYSES

Population PK/PD modeling will be used to explore the relationship between lorcaserin plasma exposure and response, including but not limited to change in BMI from baseline and the probability of achieving at least a 5% and at least a 10% change in BMI from baseline to Week 52. Additionally, exposure-safety relationships for select safety parameters may be explored graphically, depending on the data at the end of study. Any emergent relationship may be modeled as appropriate. Any parameters based on the study data may be considered for exploratory assessment for its relationship to PK.

9.7.1.7.4 PHARMACOGENOMIC AND PHARMACOGENETIC ANALYSES

Not applicable

9.7.1.8 Safety Analyses

Evaluations of safety will be performed on the Safety Analysis Set. Safety assessments including the incidence of AEs (including changes from baseline in physical examination, neuromuscular sign assessment for serotonin syndrome, and signs and symptoms of priapism and hyperprolactinemia), out-of-normal-range laboratory safety test values, change from baseline in laboratory safety test values, ECGs, vital sign measurements, bone mineral density and content, total body fat mass and total body lean mass by DEXA, FDA-defined valvulopathy, and pulmonary hypertension by echocardiograph will be summarized by treatment group using descriptive statistics or frequency count as appropriate. (revised per Amendments 01, 03, and 04)

No hypothesis testing will be performed for the safety assessment.

Study Day 1 for all safety analyses will be defined as the date of the first dose of study drug.

9.7.1.8.1 EXTENT OF EXPOSURE

Subjects will receive Belviq XR 20 mg or placebo QD for up to 52 weeks. The extent of exposure will be characterized by duration of exposure (in weeks) for each treatment group.

Duration of exposure will be defined as the number of weeks between the date the subject received the first dose of study drug and the date the subject received the last dose of study

drug. Duration of exposure will be summarized using descriptive statistics by treatment group. In addition, the duration of exposure will be categorized and will be summarized using frequency count by treatment group.

9.7.1.8.2 ADVERSE EVENTS

The AE verbatim descriptions (investigator terms from the CRF) will be classified into standardized medical terminology using the Medical Dictionary for Regulatory Activities (MedDRA). Adverse events will be coded to the MedDRA (Version 18.0 or higher) lower level term closest to the verbatim term. The linked MedDRA PT and primary system organ class (SOC) are also captured in the database.

A treatment-emergent AE (TEAE) is defined as an AE that emerges during treatment (up to 28 days after the last dose of study drug), having been absent at pretreatment (baseline) or

- Reemerges during treatment (up to 28 days after the last dose of study drug), having been present at pretreatment (baseline) but stopped before treatment, or
- Worsens in severity during treatment relative to the pretreatment state, when the AE is continuous.

Only those AEs that were treatment emergent will be included in summary tables. All AEs, treatment emergent or otherwise, will be presented in subject data listings.

The TEAEs will be summarized by treatment group. The following summaries will be reported for TEAES:

- Incidence of TEAEs in descending order of frequency
- Incidence of TEAEs by SOC and PT
- Incidence of treatment-related TEAEs by SOC and PT
- Incidence of TEAEs by SOC, PT and maximum severity (mild, moderate, or severe)
- Incidence of treatment-related TEAEs by SOC, PT, and maximum severity (mild, moderate, or severe)
- Incidence of TEAEs by SOC, PT, and relationship to study drug (Yes [related] or No [not related])

A subject will be counted only once within a SOC or PT, if the subject experienced more than 1 TEAE within a specified SOC and PT.

The following summaries will also be presented for the treatment-emergent SAEs.

- Incidence of TEAEs leading to death
- Incidence of treatment-emergent SAE by SOC and PT
- Incidence of treatment-related treatment-emergent SAE by SOC and PT

In addition, subjects with TEAEs leading to discontinuation from study drug and AEs of special interest as described in [Section 9.5.4.3.2](#) will be summarized by MedDRA SOC and PT for each treatment group.

9.7.1.8.3 LABORATORY VALUES

Laboratory results will be summarized using Système International units, as appropriate. For all quantitative parameters listed in [Section 9.5.1.5.3](#), the actual value and the change from baseline to each postbaseline visit and to the end of treatment (defined as the last on-treatment value) will be summarized by visit and treatment group using descriptive statistics. Percentages will be based on the number of subjects with both nonmissing baseline and relevant postbaseline results.

Laboratory test results will be assigned a low/normal/high (LNH) classification according to whether the value was below (L), within (N), or above (H) the laboratory parameter's reference range. Within-treatment comparisons for each laboratory parameter will be based on 3-by-3 tables (shift tables) that compare the baseline LNH classification to the LNH classification at the End of Treatment and the Follow-Up visits. Similar shift tables will also compare the baseline LNH classification to the LNH classification for the highest and lowest value during the treatment period.

[Appendix 1](#) presents the criteria that will be used to identify subjects with treatment-emergent markedly abnormal laboratory values (TEMAV). Except for phosphate, a TEMAV is defined as a postbaseline value with an increase from baseline to a grade of 2 or higher. For phosphate, a TEMAV was defined as a postbaseline value with an increase from baseline to a grade of 3 or higher. When displaying the incidence of TEMAVs, each subject may be counted once in the laboratory parameter high and in the laboratory parameter low categories, as applicable.

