9.5.5 Completion/Discontinuation of Subjects

The investigator may withdraw the subject from the study at any time for safety or administrative reasons. A subject may elect to discontinue the study at any time for any reason. All subjects will continue in the study until the 52-week evaluation is completed. Subjects who discontinue study drug prematurely will continue to be evaluated for all study assessments until study completion. All attempts will be made to capture height and weight in all subjects whether or not they are still on IP at the end of the study. All subjects who discontinue the study are to complete the study's early discontinuation procedures indicated in the Schedule of Procedures/Assessments [Table 2](#)). (revised per Amendment 03)

The investigator will promptly explain to the subject involved that the study will be discontinued for that subject and provide appropriate medical treatment and other necessary measures for the subject. A subject who has ceased to return for visits will be contacted by mail, phone, or other means to gather information such as the reason for failure to return, the status of treatment compliance, the presence or absence of AEs, and clinical courses of signs and symptoms.

Subjects who discontinue early from the study will be discontinued for 1 of these primary reasons: AE(s), lost to follow-up, subject choice, withdrawal of consent, pregnancy, study terminated by sponsor, or other. In addition to the primary reason, the subject may indicate 1 or more of the secondary reasons for discontinuation. Study disposition information will be collected on the Subject Disposition CRF. If “lost to follow-up” is recorded in clinical database, appropriate queries will be sent to investigators in order to collect all the relevant reasons for missing data. (revised per Amendment 03)

Every effort, including proper training of all study participants and their parent/guardian, should be made in order to achieve optimal subject retention and prevent missing data, especially for the Week 52 primary endpoint. A retention plan to help avoid missing data will be developed and included in study manual. (revised per Amendment 03)

A subject removed from the study for any reason may not be replaced.

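### Treatment-emergent abnormal laboratory values are defined with no limit after the last dose, although subjects who stop drug early stay under laboratory follow-up

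*Protocol*

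**What the plan says.** Protocol Section 9.7.1.8.3 introduces criteria for "treatment-emergent markedly abnormal laboratory values (TEMAV"). For every parameter except phosphate, "a TEMAV is defined as a postbaseline value with an increase from baseline to a grade of 2 or higher". The phosphate rule differs only in its grade: "For phosphate, a TEMAV was defined as a postbaseline value with an increase from baseline to a grade of 3 or higher". Neither sentence refers to the last dose.

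Section 9.7.1.8.2, immediately before it, defines a treatment-emergent adverse event as "an AE that emerges during treatment (up to 28 days after the last dose of study drug") and absent before treatment. It has parallel clauses for events that re-emerge or worsen.

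Section 9.5.5 sets the follow-up: "Subjects who discontinue study drug prematurely will continue to be evaluated for all study assessments until study completion". The schedule (Table 2) and the blood-volume table (Table 3) place routine laboratory tests after baseline at Visits 3, 4, 6, 8 and 11 and at End of Study, which are Weeks 1, 5, 12, 28, 52 and 56.

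**The concern.** An open-ended postbaseline rule does no harm when sampling stops with treatment. Here it does not. Someone who stops drug in the first months and stays in the study goes on giving samples to Week 56, and any of them that reaches the grade is labelled treatment-emergent.

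The label then says something the rule does not deliver. A reader of the incidence table would take its counts as abnormalities arising on or shortly after drug, when some could come from samples taken many months off drug. The laboratory table and the adverse-event table would also use the same term with different time limits.

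The protocol fixes this definition itself. An analysis plan that follows it carries the problem forward, and one that adds a window departs from the protocol.

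**Working it through.** The protocol gives no figure on this point, so there is none to reproduce. The check has two parts.

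**1. Which scheduled samples are affected**

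Inputs: routine laboratory weeks 1, 5, 12, 28, 52 and 56 (Tables 2 and 3); treatment for up to 52 weeks (Section 9.7.1.8.1); the 28-day, or 4-week, window from Section 9.7.1.8.2. For a last dose at week L, a laboratory visit at week t lies outside the adverse-event window when t − L > 4. All visits are taken at their nominal times.

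- L = 1: 4 of 5 later visits are outside, at 11, 27, 51 and 55 weeks after the last dose (Week 5 falls exactly on day 28 and is inside).
- L = 5: 4 of 4, at 7, 23, 47 and 51 weeks.
- L = 8: 3 of 4, at 20, 44 and 48 weeks (Week 12 falls exactly on day 28).
- L = 12: 3 of 3, at 16, 40 and 44 weeks.
- L = 20: 3 of 3, at 8, 32 and 36 weeks.
- L = 28: 2 of 2, at 24 and 28 weeks.
- L = 36: 2 of 2, at 16 and 20 weeks.
- L = 44: 2 of 2, at 8 and 12 weeks.
- L = 52: 0 of 1, because 56 − 52 = 4 weeks, exactly day 28.

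In general, Weeks 52 and 56 are both outside whenever L + 4 < 52. Every last dose from Week 1 to Week 44 therefore leaves at least two such visits.

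The completer's result depends on timing. Table 2 allows ±7 days for all visits. With a last dose at nominal Week 52 and an End of Study visit 7 days late, the sample falls on day 28 + 7 = 35.

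**2. How the rule compares with its neighbours**

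- Adverse events (9.7.1.8.2): limited to 28 days after the last dose.
- Laboratory change from baseline (9.7.1.8.3): taken to "the end of treatment (defined as the last on-treatment value").
- Laboratory shift tables for extremes (9.7.1.8.3): use "the LNH classification for the highest and lowest value during the treatment period". Even if that means the scheduled 52-week period and not actual time on drug, it has an end.
- QTc threshold counts (9.7.1.8.5): start from the maximum postbaseline value but are tabulated for the time on treatment.
- TEMAV (9.7.1.8.3): no limit.

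The only one of these summaries named treatment-emergent in the laboratory section is the one without a time limit.

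**The case against.** The strongest reply is that on-treatment date flags for laboratory data are usual content of an analysis plan, that Section 9.7.1 defers further detail to that plan, and that the label already signals the intent. This would answer a silent protocol. Here the protocol states the counting rule in full, and the rule as written admits any postbaseline value.

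Other parts of the reply stand:

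- Section 9.7.1.8.2 governs adverse events only. A different rule for laboratory values is an inconsistency in the use of one term, not a contradiction.
- The two tables need not match in any case. Under Section 9.5.1.5.1 a laboratory abnormality becomes an adverse event through intervention, withdrawal or withholding of drug, or the investigator's judgment.
- The section already offers displays with on-treatment limits, and Section 9.7.1.8 plans no hypothesis testing for safety.

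A reader might infer that off-drug values dilute the contrast between arms and so hide harm. The protocol does not support this. Suppose, hypothetically, on-drug rates of 10% and 5% with 3 points of off-drug abnormalities added to each arm. The rates become 13% and 8%. The ratio falls from 2.0 to 1.6, but the difference stays at 5 points. The 3 points have no source, and unequal stopping or late effects could move the contrast either way.

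A reader might also use the 40% dropout rate in Section 9.7.2 to size the problem. That is a planning assumption about dropout, not a rate of stopping drug while remaining under observation. Subjects who leave the study contribute no later samples.

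**Conclusion.** The point holds as a minor defect in a stated definition. Followed as written, the rule counts laboratory values taken well beyond 28 days off drug as treatment-emergent. At nominal visit times this applies to at least two scheduled visits for any last dose from Week 1 to Week 44, and to none for a Week 52 completer.

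The count rests on the schedule and on subjects staying in follow-up after stopping, as Section 9.5.5 requires. The protocol does not say how many subjects will do so, so neither the share of affected values nor the size or direction of any distortion can be computed. The consequence is confined to one descriptive incidence table. The primary and key secondary analyses are not touched.

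**What to change.** In Section 9.7.1.8.3, define a TEMAV as a value obtained after the first dose and no later than 28 days after the last dose, with an increase from baseline to Grade 2 or higher (Grade 3 or higher for phosphate). This borrows the protocol's own adverse-event window. State how a completer's Week 56 sample is classed, since it falls on day 28 at nominal timing and can fall later within the ±7-day visit window. Tabulate later values separately as post-treatment.

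The cost is a short addition to the text, one date condition in programming and one further display. No procedure or sampling changes. The small downside is that delayed abnormalities leave the TEMAV incidence table; the separate post-treatment table keeps them visible.
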